7.2 Clinical Laboratory Data

Descriptive statistics for clinical laboratory values (in SI units) and changes from baseline at each assessment time point as well as shift tables from baseline to each visit for quantitative variables will be presented by treatment group for the following clinical laboratory parameters:

Hematology Hemoglobin, hematocrit, red blood cells, platelet count, white blood cell count – total and differential, total neutrophils (absolute), eosinophils (absolute), monocytes (absolute), basophils (absolute) and lymphocytes (absolute).

Biochemistry Sodium, potassium, glucose, blood urea nitrogen, creatinine, calcium, chloride, phosphorus, total protein, total CO₂ (bicarbonate), albumin, aspartate transaminase, alanine transaminase, gamma glutamyl transferase, alkaline phosphatase, total bilirubin, and uric acid.

Urinalysis pH, glucose, protein, blood, ketones, bilirubin, nitrites, leukocyte esterase, and specific gravity.

Clinical laboratory test values are potentially clinically important (PCI) if they meet either the low or high PCI criteria listed in [Table 1](#). The number and percentage of subjects with post-baseline PCI values will be tabulated overall. The percentages will be calculated relative to the number of subjects with available baseline values and at least 1 post-baseline assessment. The numerator is the total number of subjects with at least

1 post-baseline PCI value. A supportive listing of subjects with post-baseline PCI values will be provided including the subject number, baseline, and post-baseline values.

Table 1: Criteria for Potentially Clinically Important Laboratory Tests

Parameter	Classification	Criteria: SI Units (Conventional Units)
Hematology		
Hemoglobin	LOW and DECREASE	<100 g/L (10g/dL) AND Decrease of ≥ 20 g/L (2.0 g/dL) from baseline value
	HIGH	>200 g/L (20g/dL)
Hematocrit	LOW and DECREASE	$\leq 0.6 \times$ LLN AND Decrease of ≥ 0.06 L/L (6.0%) from baseline value
	HIGH	$>1.3 \times$ ULN
Red blood cells count	LOW	$<3 \times 10^{12}/L$
	HIGH	$>7.5 \times 10^{12}/L$
Platelet count	LOW	$<0.6 \times$ LLN OR $<100 \times 10^9/L$ ($100 \times 10^3/\mu L$)
	HIGH	$>1.5 \times$ ULN OR $>500 \times 10^9/L$ ($500 \times 10^3/\mu L$)
White blood cell count	LOW	$<0.5 \times$ LLN OR $<3.0 \times 10^9/L$ ($3 \times 10^3/\mu L$)
	HIGH	$>2 \times$ ULN OR $>16.0 \times 10^9/L$ ($16 \times 10^3/\mu L$)
Neutrophils	LOW	$<1.5 \times 10^9/L$ ($1.5 \times 10^3/\mu L$) OR $< 40\%$

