### 4.1 Inclusion Criteria

The subject will not be considered eligible for the study without meeting all of the criteria below.

Subjects cannot be enrolled before all inclusion criteria (including test results) are confirmed.

1. Has given, personally signed, and dated informed consent to participate in the study, in accordance with the International Conference on Harmonization Good Clinical Practice Guideline E6 (1996) and applicable regulations, before completing any study-related procedures.
2. Age 18-45 years inclusive at the time of consent. The date of signing informed consent is defined as the beginning of the Screening Period. This inclusion criterion will be assessed only at the Screening Visit.
3. Male, or non-pregnant, non-lactating female who agrees to comply with any applicable contraceptive requirements of the protocol or females of non-childbearing potential. A female of non-childbearing potential (defined as a female who is post-menopausal [amenorrhea for at least 12 consecutive months], has had a hysterectomy, bilateral tubal ligation, bilateral oophorectomy or bilateral salpingectomy).
4. Satisfactory medical assessment with no clinically significant or relevant abnormal findings as determined by medical/surgical history, physical examination, vital signs, 12-lead electrocardiogram, and clinical laboratory evaluation (hematology, biochemistry, thyroid function, and urinalysis) that are likely to interfere with the subject's participation or ability to complete the study as assessed by the investigator.
5. An understanding, ability, and willingness to fully comply with study procedures and restrictions.
6. Body mass index (BMI) between 18.5 and 30.0 kg/m^2 inclusive; assessed only at the screening visit.
7. Able to swallow (multiple capsules or tablets at 1 time or consecutively at 1 time) all investigational product.
8. Healthy as determined by the investigator on the basis of screening evaluations.

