7.3 Vital Signs

Descriptive statistics for vital signs (systolic and diastolic blood pressure and pulse rate) and their changes from baseline at each post-baseline visit and at end of study will be presented by treatment group.

Vital sign values will be considered PCI if they meet both the observed value criteria and the change from baseline criteria listed in Table 2. The number and percentage of subjects with PCI post-baseline values will be tabulated by time point and treatment group. The percentages will be calculated relative to the number of subjects with baseline and available assessment at that time point in that treatment group. The numerator is the total number of subjects with at least 1 PCI post-baseline vital sign value at that time point in that treatment group. A supportive listing of subjects with post-baseline PCI values will be provided including the subject number, baseline, and post-baseline PCI values.

Table 2: Criteria for Potentially Clinically Important Vital Signs

Parameter	Classification	Criteria
Sitting and Supine		
Systolic BP (mmHg)	LOW and DECREASE	≤90 and decrease of ≥20 from baseline value
	HIGH and INCREASE	≥140 and increase of ≥20 from baseline value
Diastolic BP (mmHg)	LOW and DECREASE	≤50 and decrease of ≥15 from baseline value
	HIGH and INCREASE	≥90 and increase of ≥15 from baseline value
Pulse rate (bpm)	LOW and DECREASE	≤45 and decrease of >15 from baseline value
	HIGH and INCREASE	≥100 and increase of >15 from baseline value
Temperature (regardless of method)	LOW	<35°C or <95°F
	HIGH	>38.3°C or >100.9°F
Respiratory rate (breaths/min)	LOW	<10
	HIGH	>25

Abbreviations: BP=blood pressure, bpm=beats per minute.

All vital signs data will be listed for the Safety Set.

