7.4 Electrocardiogram (ECG)

Descriptive statistics for ECG variables (heart rate, PR, RR, QRS, QT, and QTc intervals) and their changes from baseline at each time point will be presented by treatment group. QTc interval will be calculated using both Bazett ($QTcB=QT/(RR)^{1/2}$) and Fridericia ($QTcF=QT/(RR)^{1/3}$) corrections; and if RR is not available, it will be replaced with $60/(\text{heart rate})$ in the correction formula. The ECG interpretation at each time point will be summarized by treatment group. A shift table from baseline to each time point for qualitative ECG results will be presented by treatment group.

Electrocardiogram variable values will be considered PCI if they meet or exceed the upper limit values listed in Table 3. The number and percentage of subjects with post-baseline PCI values will be tabulated by treatment and time point. The percentages will be calculated relative to the number of subjects with available non-PCI baseline and available assessment at that time point in that treatment group. The numerator is the total number of subjects with at least 1 PCI post-baseline ECG value at that time point in that treatment group. A listing of all subjects with post-baseline PCI value will be provided including the subject number, baseline, and post-baseline PCI values.

Table 3: Criteria for Potentially Clinically Important ECG Values

Parameter	Classification	Criteria
Overall evaluation	ABNORMAL	Overall evaluation is ABNORMAL
Rhythm	NON-SINUS RHYTHM	Rhythm is not SINUS
Heart rate (bpm)	LOW and DECREASE	≤45 and decrease of >15 from baseline value
	HIGH and INCREASE	≥100 and increase of >15 from baseline value
PR interval (msec)	HIGH and INCREASE	≥200 and increase of ≥20 from baseline value
QRS interval (msec)	HIGH	≥120
QTc interval (men) (msec)*	HIGH	>430 and increase from baseline value >30
QTc interval (women) (msec)*	HIGH	>450 and increase from baseline value >30

Abbreviations: bpm=beats per minute; QTc=QT interval corrected.

*Values noted refer to both Bazett's (QTcB) and Fridericia's (QTcF) formula

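### The laboratory PCI percentage in SAP 7.2 includes subjects who were already beyond the cut-off before dosing, because the denominator accepts any baseline and most Table 1 criteria carry no change term

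*SAP*

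**What the plan says.** SAP 7.2 treats a laboratory value as PCI "if they meet either the low or high PCI criteria listed in" SAP Table 1. On presentation it says: "The number and percentage of subjects with post-baseline PCI values will be tabulated overall". The denominator rule is: "The percentages will be calculated relative to the number of subjects with available baseline values and at least 1 post-baseline assessment". One PCI value after baseline is enough to enter the numerator; the rule closes, and the listing is described, in these words: "1 post-baseline PCI value. A supportive listing of subjects with post-baseline PCI values will be provided including the subject number, baseline, and post-baseline values". SAP 11.3 adds that all post-baseline assessments, including repeats and unscheduled ones, count towards PCI.

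Some Table 1 rows join a level to a change, for example those classed "LOW and DECREASE". Most do not.

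The two neighbouring sections are written differently. In SAP 7.3 a vital sign is PCI only if it should "meet both the observed value criteria and the change from baseline criteria". In SAP 7.4 the ECG percentages are taken "relative to the number of subjects with available non-PCI baseline and available assessment at that time point".

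Entry sets no numeric laboratory limits. Inclusion criterion 4 in Protocol 4.1 asks for "Satisfactory medical assessment with no clinically significant or relevant abnormal findings" likely to interfere with participation or completion, as judged by the investigator.

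**The concern.** A table of post-baseline PCI values will usually be read as showing what appeared after dosing. On a level-only row, the SAP 7.2 rule does not separate a subject who crossed the cut-off after dosing from one who was beyond it all along. The entry criterion allows the second kind of subject, since a value can lie beyond a Table 1 cut-off without being judged clinically significant.

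Change in laboratory results from baseline is part of the secondary safety endpoint in the Protocol synopsis. The study has about 20 subjects and no parallel control arm, so each subject counted is worth 5 percentage points. Because laboratory PCI is tabulated overall, while vital signs and ECGs are tabulated by treatment group and time point, the table gives no timing from which a reader could infer that a value was pre-existing.

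**Working it through.** The plan states no expected PCI rate, so there is no figure to reproduce.

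**1. Count of criteria in SAP Table 1** (each low or high classification counted once)

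- With a change term: hemoglobin low, hematocrit low, potassium (2), creatinine, calcium (2), total protein (2), albumin (2), uric acid (2). Total 1+1+2+1+2+2+2+2 = 13.
- Hematology without one: hemoglobin high, hematocrit high, red cells (2), platelets (2), white cells (2), neutrophils (2), eosinophils, monocytes, basophils, lymphocytes (2) = 15.
- Biochemistry without one: sodium (2), glucose (2), urea nitrogen, phosphorus (2), AST, ALT, GGT, alkaline phosphatase, bilirubin = 12.
- Thyroid tests without one = 6; urinalysis without one = 7.

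Level-only total: 15+12+6+7 = 40 of 53. The schedule shows TSH and T4 at screening only; without the thyroid rows the count is 34 of 47. Several level-only rows use multiples of, or offsets from, the laboratory's normal limits rather than fixed numbers, but they still test level alone.

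**2. The unchanged subject**

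SAP Tables 5 and 6 schedule three post-baseline draws: Day 1 at 12 h, Day 8 pre-dose and Day 8 at 24 h. Let q be the chance that one draw lies beyond the cut-off. With no drug effect and independent within-subject noise, P(counted) = 1 − (1 − q)³.

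- True value exactly at the cut-off: q = 0.5, so 1 − 0.5³ = 0.875.
- True value one within-subject SD beyond it: q = 0.841, so 1 − 0.159³ = 0.996.
- Value beyond the cut-off that never moves: q = 1, so always counted. This case needs no variability assumption.

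If two of 20 subjects are beyond a level-only cut-off before dosing and stay there, and nobody else crosses it, SAP 7.2 reports 2/20 = 10%. Restricting numerator and denominator to non-PCI baselines gives 0/18 = 0%, with 2 shown as PCI at baseline.

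**3. Illustrative size**

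The documents give no means or SDs, so these inputs are assumptions. The model has no treatment effect, one baseline and three post-baseline draws, and normal between- and within-subject variation; 400,000 subjects were simulated per setting.

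Neutrophil percentage, cut-offs 40 and 70, mean 56:

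| Total SD | Intra-subject correlation | Flagged under SAP 7.2 | Of these, PCI at baseline | Flagged among non-PCI baselines |
|---|---|---|---|---|
| 8 | 0.7 | about 13% | 28% | about 10% |
| 10 | 0.85 | about 23% | about 48% | about 14% |

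Over SD 6-10 and correlation 0.5-0.85, the share already PCI at baseline runs from roughly 10% to 50%.

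Arithmetic check of the first line: P(PCI at baseline) = Φ(−2) + Φ(−1.75) = 0.023 + 0.040 = 0.063. The rate among non-PCI baselines is then 13% × (1 − 0.28) / (1 − 0.063) = 10.0%. In 20 subjects, 13% is 2.6 flagged, of whom 0.28 × 2.6 = 0.7 were PCI beforehand.

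A generic one-sided row with its cut-off at the 97.5th percentile behaves similarly. For between-subject variance shares of 0.5, 0.7 and 0.9, SAP 7.2 flags 6.2%, 5.5% and 4.3%; 16%, 26% and 47% of those were PCI at baseline; and the rate among non-PCI baselines is 5.3%, 4.1% and 2.3%.

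**The case against.** The strongest reply is that the same section already supplies what a reader needs. SAP 7.2 plans change-from-baseline statistics and shift tables by treatment group, and the PCI listing prints the baseline beside the post-baseline values. With about 20 subjects, an unmoved abnormality can be found by eye. The table also claims only to count post-baseline PCI values, not new ones, and an over-inclusive screen is a legitimate safety tool. All of this stands and limits the weight of the point. It does not change the percentage itself, and the SAP gives no reason for treating laboratory values differently from ECGs.

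Three stronger readings are tempting, and the documents do not support them.

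- A reader might infer that the PCI table is the main laboratory safety result. Protocol 9.9 introduces PCI findings as an additional summary or listing, and no test or decision rule uses them.
- A reader might infer that random variation alone accounts for the flags and that a baseline restriction would remove it. No variability is given, and in the illustration the restriction only moves about 13% to about 10%. It removes pre-existing cases and leaves most chance crossings.
- A reader might infer that a second, confirming draw should therefore be required. The three scheduled draws fall under anagrelide alone, omeprazole alone and the combination. An effect first seen after co-administration has one scheduled draw and would be missed unless an unscheduled repeat was taken.

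**Conclusion.** The point holds in a limited form and the SAP should be changed. SAP 7.2 counts subjects whose PCI value predates dosing, on the 40 of 53 criteria (34 of 47 without thyroid tests) that have no change term. It does not affect the 13 criteria that require a change, or the primary pharmacokinetic analysis. How many subjects are involved cannot be derived from the documents. Under the assumed neutrophil settings it is roughly 10-50% of those flagged, and less than one subject in 20 at the central setting. Rows with more extreme limits, such as transaminases above twice the upper limit of normal, were not simulated and would be expected to contribute less in healthy volunteers. That a subject beyond a level-only cut-off whose value never moves is always counted follows from the text alone.

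**What to change.** In SAP 7.2, state that for each parameter and direction both the numerator and the denominator are restricted to subjects whose baseline does not already meet that criterion's level cut-off. Show the number PCI at baseline in an adjacent column. Keep all subjects, including those PCI at baseline, in the supportive listing and the shift tables.

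Name both parts of the fraction. The ECG sentence in SAP 7.4 restricts only the denominator explicitly; copied as it stands into the example above, it could be read as 2/18 = 11%, which is worse than the present rule.

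The cost is one sentence and one column in the table shell, with no new data. The downside is that a subject who is PCI at baseline and then worsens leaves the percentage. That subject stays in the listing with both values, and the added column shows how many subjects the restriction sets aside.

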Abbreviations: LLN=lower limit of normal value provided by the laboratory, ULN=upper limit of normal value provided by the laboratory

All laboratory data will be listed for the Safety Set.

7.3 Vital Signs

Descriptive statistics for vital signs (systolic and diastolic blood pressure and pulse rate) and their changes from baseline at each post-baseline visit and at end of study will be presented by treatment group.

Vital sign values will be considered PCI if they meet both the observed value criteria and the change from baseline criteria listed in Table 2. The number and percentage of subjects with PCI post-baseline values will be tabulated by time point and treatment group. The percentages will be calculated relative to the number of subjects with baseline and available assessment at that time point in that treatment group. The numerator is the total number of subjects with at least 1 PCI post-baseline vital sign value at that time point in that treatment group. A supportive listing of subjects with post-baseline PCI values will be provided including the subject number, baseline, and post-baseline PCI values.

Table 2: Criteria for Potentially Clinically Important Vital Signs

Parameter	Classification	Criteria
Sitting and Supine		
Systolic BP (mmHg)	LOW and DECREASE	≤90 and decrease of ≥20 from baseline value
	HIGH and INCREASE	≥140 and increase of ≥20 from baseline value
Diastolic BP (mmHg)	LOW and DECREASE	≤50 and decrease of ≥15 from baseline value
	HIGH and INCREASE	≥90 and increase of ≥15 from baseline value
Pulse rate (bpm)	LOW and DECREASE	≤45 and decrease of >15 from baseline value
	HIGH and INCREASE	≥100 and increase of >15 from baseline value
Temperature (regardless of method)	LOW	<35°C or <95°F
	HIGH	>38.3°C or >100.9°F
Respiratory rate (breaths/min)	LOW	<10
	HIGH	>25

Abbreviations: BP=blood pressure, bpm=beats per minute.

All vital signs data will be listed for the Safety Set.

7.4 Electrocardiogram (ECG)

Descriptive statistics for ECG variables (heart rate, PR, RR, QRS, QT, and QTc intervals) and their changes from baseline at each time point will be presented by treatment group. QTc interval will be calculated using both Bazett ($QTcB=QT/(RR)^{1/2}$) and Fridericia ($QTcF=QT/(RR)^{1/3}$) corrections; and if RR is not available, it will be replaced with $60/(\text{heart rate})$ in the correction formula. The ECG interpretation at each time point will be summarized by treatment group. A shift table from baseline to each time point for qualitative ECG results will be presented by treatment group.

Electrocardiogram variable values will be considered PCI if they meet or exceed the upper limit values listed in Table 3. The number and percentage of subjects with post-baseline PCI values will be tabulated by treatment and time point. The percentages will be calculated relative to the number of subjects with available non-PCI baseline and available assessment at that time point in that treatment group. The numerator is the total number of subjects with at least 1 PCI post-baseline ECG value at that time point in that treatment group. A listing of all subjects with post-baseline PCI value will be provided including the subject number, baseline, and post-baseline PCI values.

Table 3: Criteria for Potentially Clinically Important ECG Values

Parameter	Classification	Criteria
Overall evaluation	ABNORMAL	Overall evaluation is ABNORMAL
Rhythm	NON-SINUS RHYTHM	Rhythm is not SINUS
Heart rate (bpm)	LOW and DECREASE	≤45 and decrease of >15 from baseline value
	HIGH and INCREASE	≥100 and increase of >15 from baseline value
PR interval (msec)	HIGH and INCREASE	≥200 and increase of ≥20 from baseline value
QRS interval (msec)	HIGH	≥120
QTc interval (men) (msec)*	HIGH	>430 and increase from baseline value >30
QTc interval (women) (msec)*	HIGH	>450 and increase from baseline value >30

Abbreviations: bpm=beats per minute; QTc=QT interval corrected.

*Values noted refer to both Bazett's (QTcB) and Fridericia's (QTcF) formula

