  - History of controlled or uncontrolled hypertension or a systolic blood pressure  $\geq 140$  mmHg or diastolic blood pressure  $\geq 90$  mmHg at the Screening Visit or Day -1.
  - Subject has any history of seizure disorder.
  - History or presence of known structural cardiac abnormalities, syncope, cardiac conduction problems (PR interval  $> 220$  ms, second or third-degree heart block, bundle branch block [except congenital right bundle branch block], or prolonged QTc interval) or exercise-related cardiac events.
  - History of alcohol or other substance abuse within the last year.
7. A subject's alcohol consumption that fulfils one of the following: (Note: One alcohol unit=1 beer [12 oz]=1 wine [5 oz]=1 liquor [1.5 oz])
    - Has consumed alcohol within 2 days prior to the first dose of investigational product.
    - Male subjects who consume more than 3 units\* of alcohol per day.
    - Female subjects who consume more than 2\* units of alcohol per day.
  8. Positive screening test results for alcohol, drugs of abuse, or pregnancy (females of childbearing potential only) at the Screening Visit or Day -1.
  9. A positive human immunodeficiency virus (HIV) antibody screen, hepatitis B surface antigen (HBsAG) or hepatitis C virus antibody (HCV) screen.
  10. Use of tobacco in any form (eg, smoking or chewing) or other nicotine-containing products in any form (eg, gum, patch) within 30 days prior to the first dose of investigational product and during the in-house stay at the CRC.
  11. A positive urine cotinine test that is  $\geq 50$  ng/mL at either the Screening Visit or on Day -1.
  12. Routine consumption of more than 2 units of caffeine per day or subjects who experience caffeine-withdrawal headaches or have a history of caffeine-withdrawal headaches. (One caffeine unit is contained in the following items: one 6-oz cup of coffee, two 12-oz cans of cola, one 12-oz cup of tea, and three 1-oz chocolate bars. Decaffeinated coffee, tea, or cola are not considered to contain caffeine.)
  13. Consumption of grapefruit, Seville oranges, and/or products containing these items within 7 days prior to the first dose of investigational product.
  14. Donation of blood or blood products (egg, plasma, or platelets) within 60 days prior to the first dose of investigational product.

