### 7.2.2.9 Electrocardiogram

Twelve-lead ECGs will be performed at the times specified in [Table 1](#), [Table 2](#), and [Table 3](#) using the standard methods/equipment at the CRC.

The following parameters will be recorded on the appropriate CRF page: heart rate, PR, RR, QRS, and QT intervals. The QTcB and QTcF will be derived from the data in the database. The investigator's assessment of the ECG tracing as normal or abnormal must be documented, and if abnormal, his/her determination of whether the abnormality is clinically significant or not will be documented on the tracing and recorded in the CRF.

The subject should be asked to remove all clothing that covers the location of lead placement. The subject must be resting in the supine position for at least 5 minutes prior to collecting the ECG.

In some cases, it may be appropriate to repeat abnormal ECGs to rule out improper lead placement as contributing to the ECG abnormality. It is important that leads are placed in the same positions each time in order to achieve precise ECG recordings.

One complete recording, including a 10-second rhythm strip, should be taken at each time point. It should be immediately assessed as a valid recording and if not valid, it should be repeated. Invalid recordings will not be entered in the CRF. The ECG collected predose on Day 1 will serve as the subject's baseline ECG.

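### The ECG PCI percentage in SAP 7.4 counts persisting baseline findings in the numerator but removes them from the denominator, and does not define a non-PCI baseline for criteria with a change term

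*SAP*

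**What the plan says.** SAP 7.4 builds the ECG PCI table from two consecutive sentences. The denominator is restricted by baseline status: "The percentages will be calculated relative to the number of subjects with available non-PCI baseline and available assessment at that time point". The numerator is not: "The numerator is the total number of subjects with at least 1 PCI post-baseline ECG value at that time point".

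A value is classed as PCI by this rule: "Electrocardiogram variable values will be considered PCI if they meet or exceed the upper limit values listed in Table 3". SAP Table 3 then lists two kinds of criteria:

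- **No change term:** overall evaluation abnormal, rhythm not sinus, QRS at or above 120 msec.
- **Limit plus change from baseline:** heart rate, PR and QTc.

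The corresponding vital-signs percentage in SAP 7.3 has no baseline restriction; it is taken "relative to the number of subjects with baseline and available assessment at that time point in that treatment group". The laboratory percentage in SAP 7.2 also uses subjects with any available baseline.

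SAP 7.4 plans other ECG displays as well. One is a shift table: "A shift table from baseline to each time point for qualitative ECG results will be presented by treatment group". Another is a listing of subjects with post-baseline PCI values that shows their baseline values.

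**The concern.** A percentage of subjects needs a numerator drawn from its denominator. Limiting the denominator to subjects with a non-PCI baseline implies that the table is meant to show new findings. The numerator sentence does not carry that limit. Followed literally, the two sentences mix new and persisting findings over a base from which the persisting ones have been removed.

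A harmless ECG feature that was present before dosing could therefore appear as a non-zero PCI rate under each treatment, and the PCI table could disagree with the shift table in the same section.

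The second gap is related. The change of a baseline value from itself is zero, so the SAP needs to say whether a baseline can be PCI at all on heart rate, PR or QTc. It does not.

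**Working it through.** SAP 7.4 states no numerical result, so there is none to reproduce. The check is of the definition.

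**Inputs**

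- Subjects assessed: 20, the planned number of completers (SAP 3.4).
- Scheduled post-baseline ECGs: four, namely Day 1 at 12 h and Day 8 at pre-dose, 12 h and 24 h (Protocol Tables 2 and 3). Baseline is the Day 1 pre-dose ECG (Protocol 7.2.2.9).
- k = subjects with a baseline PCI finding that persists; n = subjects with a new PCI finding. Neither is in the documents. Both are assumed, with all 20 subjects assessed.

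**Step 1. Can such baselines occur?** Yes.

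- Inclusion criterion 4 (Protocol 4.1) asks for "Satisfactory medical assessment with no clinically significant or relevant abnormal findings" and goes on to limit this to findings likely to interfere with participation or completion.
- The conduction exclusion (Protocol 4.2) lists "second or third-degree heart block, bundle branch block [except congenital right bundle branch block], or prolonged QTc interval", so congenital right bundle branch block is admitted.
- Protocol 7.2.2.9 records the tracing as normal or abnormal first ("assessment of the ECG tracing as normal or abnormal must be documented, and if abnormal"), with clinical significance then judged separately. Abnormal but not clinically significant is therefore a valid baseline result.

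**Step 2. Which rows are exposed?** Those without a change term. Overall evaluation is the realistic one. A QRS at or above 120 msec should be rare in this population. Rhythm is not among the ECG parameters that Protocol 7.2.2.9 lists for the CRF, so that row may be empty.

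**Step 3. Formulas**

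- As written: (k+n)/(20−k)
- Numerator restricted to the denominator: n/(20−k)
- Denominator of the SAP 7.3 type: (k+n)/20

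The excess of the first over the second is k/(20−k), whatever n is: 1/19 = 5.3 points, 2/18 = 11.1 points, 3/17 = 17.6 points.

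| k | n | As written | Restricted numerator | 7.3-type denominator |
|---|---|---|---|---|
| 0 | 1 | 1/20 = 5.0% | 1/20 = 5.0% | 1/20 = 5.0% |
| 1 | 0 | 1/19 = 5.3% | 0/19 = 0% | 1/20 = 5.0% |
| 1 | 1 | 2/19 = 10.5% | 1/19 = 5.3% | 2/20 = 10.0% |
| 2 | 2 | 4/18 = 22.2% | 2/18 = 11.1% | 4/20 = 20.0% |
| 3 | 0 | 3/17 = 17.6% | 0/17 = 0% | 3/20 = 15.0% |

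A value above 100% needs 2k+n > 20: k of at least 11 when n=0, 10 when n=2, 9 when n=4. That is not expected, but it shows that the ratio is not a proportion.

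**Step 4. Criteria with a change term.** There are two readings of a non-PCI baseline.

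- *Full criterion.* The baseline change is zero, no baseline can be PCI, and the restriction has no effect.
- *Limit only.* A baseline beyond the limit is PCI.

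PR shows the difference. Protocol 4.2 excludes PR above 220 msec, while the Table 3 limit is 200 msec with an increase of at least 20 msec. A baseline PR of 200 to 220 msec is therefore not barred by the PR limit, and its PCI status is unclear. Suppose two subjects have such a baseline, one of them rises by 20 msec or more, and there is no other case:

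- Full criterion at baseline: 1/20 = 5.0%.
- Limit only, numerator as written: 1/18 = 5.6%.
- Limit only, numerator restricted to the denominator: 0/18 = 0%.

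**The case against.** The strongest reply is that the practical effect is small and already visible elsewhere. The one realistic row, overall evaluation, is also covered by the shift table and the PCI listing, both of which separate new from persisting findings. With about 20 subjects a reader can resolve any case by hand. The PCI count does not depend on the denominator. Every k is assumed, and healthy-volunteer eligibility makes large k unlikely. All of this stands and limits the importance of the point. It does not correct the printed percentage.

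A second reply is that 5.3% instead of 0% takes the comparator with the larger gap. Against the SAP 7.3 type of denominator, the gaps in the table above for k of 1 or more are only about 0.3 to 2.6 points. That is correct, and both comparators are shown. The restricted numerator is the more natural one here because SAP 7.4 itself chose a non-PCI baseline.

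A third reply is that the PR ambiguity is forced: Table 3 joins limit and change, so a baseline cannot meet the criterion. That is the more sensible reading, and with the numerator as written the PR example moves only from 5.0% to 5.6%. The 0/18 result appears only once the numerator is corrected. But SAP 7.3 says explicitly that both parts must be met, whereas SAP 7.4 refers to upper limit values. Anyone correcting the numerator therefore needs to settle the baseline rule as well.

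**Conclusion.** The concern holds. As written, the SAP 7.4 percentage is not a proportion whenever a subject enters with an abnormal evaluation, a non-sinus rhythm or a QRS of 120 msec or more that persists. The mismatch is specific to the ECG section; SAP 7.2 and 7.3 do not have it.

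The mismatch in the wording is certain. Its size is not known in advance: it rests on 20 subjects assessed and an assumed number of persisting findings, and it disappears if there are none. One persisting finding could affect up to four scheduled time points. The lack of a baseline rule for heart rate, PR and QTc is a lesser ambiguity, but it has to be settled together with the numerator.

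The importance is minor. The table is descriptive, and no pharmacokinetic estimate or confidence interval depends on it.

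**What to change.** Make two changes in SAP 7.4:

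1. Define the numerator as those subjects in the denominator who have a PCI value at the given time point and treatment.
2. State that, where a criterion includes a change from baseline, baseline PCI status is judged on the whole criterion, so that a high or low baseline value alone does not remove a subject from the denominator.

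The second sentence is needed with the first. Otherwise a limit-only reading could drop a real PR increase from the percentage, as in the 0/18 case.

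A simpler alternative is to delete the non-PCI restriction and use the SAP 7.3 denominator. That gives a valid proportion and removes the baseline question, but the percentage would then combine persisting and new findings.

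The cost is two sentences and, if it follows the current wording, the ECG PCI table shell. The shells are in a separate document that was not available, so whether they need changing is unknown. No new data or extra table is required.
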